11.3.3 Quality of life analysis

Quality of life will be assessed at screening and/or cycle 1 day 1 and then every 3 cycles thereafter (cycles 4, 7 and 10) using the Functional Assessment of Chronic Illness Therapy Hepatobiliary Cancer (FACIT-Hep) questionnaire. The hepatobiliary, general function, and subscale scores will

be will be graded according to the guidelines provided at http://www.facit.org. Summary statistics (e.g. means, medians, ranges) and graphical techniques (e.g. box-plots over time) will be used to summarize the patterns of scores over time and assess whether or not transformations are necessary. Comparisons of the differences in the change in scores over time between treatment groups will be performed using generalize estimating equations (GEE). Sensitivity analyses will be performed to assess the impact of missing data including best and worst case single imputation, multiple imputation. One issue when assessing quality of life is how to handle scores for individuals who have died. Some questionnaires (e.g. Stroke modified Rankin Score) include death as a value on the scale; however, this is not the case for the FACIT questionnaires. We will assess the impact of missing data due to death by assessing the worst category score for those who have died.

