4.2 Endpoints

Primary endpoint

The primary endpoint of the trial is to demonstrate an increase in the progression free survival, PFS, in resected pancreatic cancer patients treated with CC-486

Secondary endpoints

- 1) Response rate (including partial and complete response) to first line chemotherapy when given after visible disease recurrence in patients primed with CC-486 compared to observation
- 2) Overall survival
- **3)** Decreased methylation in candidate genes in the research biopsies as compared to the original resected specimens in patients treated with CC-486.
- 4) Change in quality of life scores as determined by FACIT-Hep

5 Investigational Plan

[figure not shown]

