5.2.8 Randomization

at

Subjects who are eligible to enroll in the study will be randomized in a 1:1 ratio to receive CC486 or observation. Subjects will be randomized through a computer program maintained by the study team.

- CC-486 (three 100 mg tablets on Days 1-21 every 28 days)
- Observation

The randomization will be balanced by using randomly permuted blocks and will be stratified by the following criteria:

• Positive lymph nodes at time of resection (N0 versus N1)

Approximately 55-75% of patients are expected to be node positive.^{10, 13, 40-42}

CC-486 will be packaged and designated for a patient upon randomization to Arm A. Subsequent bottles of study drug will be made available to patients as needed. Patient will receive one bottle of study drug with no more than 63 tablets in the bottle.

External sites will submit a patient enrollment log to the Coordinating Center monthly by email,

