5.3.1 Screening and Pre-Study Assessments

Screening for enrollment in this clinical trial should include a record of prior medications and anti-cancer treatments, a record of concomitant medications and procedures, medical history, a physical examination, vital signs, weight, ECOG performance status (per Appendix A), pregnancy test, labs (CBC with differential, serum chemistry and hepatic panel, CA 19-9, PT, PTT), research labs, quality of life measures and lesion assessment with CT (per Section 7). All pre-study assessments should be done ≤ 28 days from Cycle 1 Day 1.

5.3.2 Initial Phase: Assessments, Dose Modifications, and Termination 5.3.2.1 Arm A for first cycle

Prior to receiving Cycle 1 Day 1 of CC-486, patients must undergo a physical examination including vital signs, weight, and ECOG performance status assessments, and labs including CBC with differential, serum chemistry and hepatic panel, CA 19-9, PT/PTT, and research blood, a record of concomitant medications and procedures, quality of life, and an assessment of adverse events. If screening assessments were done within 7 days of initiating Cycle 1 Day 1, these do not need to be repeated. Cycle 1 of CC-486 in Arm A can then be administered on schedule if treatment criteria are met.

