11.3 Statistical Methodology

11.3.1 Efficacy Analyses

Progression free survival is defined as the time from randomization until visible recurrence on any imaging modality, a confirmed biopsy, or death. Individuals lost to follow-up prior to having an event will be censored at the time of the last scan or biopsy. In the case of an equivocal scan reading, the patient will be re-imaged on schedule, if clinically appropriate, and if subsequent reimaging confirms recurrence, the event will be considered to have occurred at the first time point when a related abnormality was noted. Overall survival is defined as the time from enrollment until death. Individuals lost to follow-up prior to death will be censored at the time of last physician contact.

Time to event outcomes, including the primary endpoint progression free survival and overall survival, will be summarized using Kaplan-Meier estimates of the survival function. From these estimates, median time to event and one-year survival proportions with 95% confidence intervals will be extracted. Cox proportional hazards models will be used to compare the two treatment arms and to evaluate and adjust for potential prognostic factors (e.g. nodal status, microscopic margins, increase in CA19-9, therapy). The number and type of responses to chemotherapy will be tabulated for each group. Logistic regression will be used to compare the response rate between the groups and to identify risk factors associated with response. Results will be considered statistically significant for p-values < 0.05.

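### Section 11.3.3 compares arms on change in FACT-Hep scores and states no adjustment for the collected baseline score or the N0/N1 stratum, so precision may be lost for no saving

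*Combined protocol and SAP*

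**What the plan says.** All references are to the combined protocol and SAP.

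- **Endpoint.** Section 4.2 lists as a secondary endpoint: "Change in quality of life scores as determined by FACIT-Hep".
- **Analysis.** Section 11.3.3: "Comparisons of the differences in the change in scores over time between treatment groups will be performed using generalize estimating equations". It gives no mean model, covariates, working correlation or constraint on the baseline means.
- **Baseline data.** Section 11.3.3: "Quality of life will be assessed at screening and/or cycle 1 day 1 and then every 3 cycles thereafter", with Cycles 4, 7 and 10 as the later visits. Section 5.3.1 includes the questionnaire in screening: "research labs, quality of life measures and lesion assessment with CT (per Section 7". The Section 2.1 schedule has it at screening for all patients and at Cycle 1 in both arms, unless already done within 7 days.
- **Stratification.** Section 5.2.8: "Subjects who are eligible to enroll in the study will be randomized in a 1:1 ratio", stratified by "Positive lymph nodes at time of resection (N0 versus N1". It adds: "Approximately 55-75% of patients are expected to be node positive".
- **Adjustment elsewhere.** Section 11.3.1 has the Cox models "evaluate and adjust for potential prognostic factors (e.g. nodal status", among other factors. Section 11.3.3 has no matching statement.
- **Missing data.** In Section 11.3.3, multiple imputation appears only among the sensitivity analyses.

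**The concern.** In a randomised comparison, baseline means differ between arms only by chance. Subtracting the whole baseline score from each follow-up score therefore adds noise whenever the correlation between the two is below 1. Regressing on baseline removes only the part that predicts follow-up, so in large samples its variance is never larger than that of the change score.

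Adverse events are collected in Arm A only (Section 6.1), which leaves this questionnaire as the main between-arm evidence on how patients feel. With at most 30 patients per arm, and fewer at later cycles, a noisier contrast makes a real worsening on CC-486 easier to miss. Leaving the model terms unstated also leaves the choice of adjustment open until the data of an open-label trial have been seen.

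**Working it through.** **Inputs.** From the documents: 30 per arm, a null median PFS of 6 months and 10% loss (11.3.4); 9.84 months under the alternative (11.3.6); a 0.05 significance level without stated sidedness (11.3.1). Assumed: two-sided 0.05, equal variances across visits, a common correlation ρ between any two scores, and a reference power of 80% for the change analysis.

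**1. The plan's own figure.** There is none for quality of life. The only power statement is for PFS, and it reproduces. Exponential event probabilities are 0.915 and 0.793 (24 months' accrual, 12 months' follow-up). With 27 per arm after 10% loss, events = 27 × (0.915 + 0.793) = 46.1. Power = Φ(ln 1.64 × √46.1 / 2 − 0.842) = 79.9%, against 80% stated.

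**2. One follow-up visit.** Variance of the change contrast ∝ 2(1 − ρ); of the baseline-adjusted contrast ∝ 1 − ρ². The ratio is (1 + ρ)/2. With 1.960 + 0.842 = 2.802, adjusted power = Φ(2.802/√ratio − 1.960).

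| ρ (assumed) | ratio | power on change (assumed) | power adjusted | gain, points |
|---|---|---|---|---|
| 0.3 | 0.65 | 80% | 93.5% | 13.5 |
| 0.5 | 0.75 | 80% | 89.9% | 9.9 |
| 0.7 | 0.85 | 80% | 86.0% | 6.0 |
| 0.8 | 0.90 | 80% | 84.0% | 4.0 |

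**3. Other starting points.** With 30 per arm, complete data and a 0.5 SD difference at one visit, power on change against adjusted is 37.3% and 52.8% (ρ 0.3), 49.1% and 60.9% (0.5), 70.5% and 77.4% (0.7), 86.5% and 89.8% (0.8). For the mean of three visits, the variances are (1 + 2ρ)/3 + 1 − 2ρ and (1 + 2ρ)/3 − ρ². The ratios are 0.475, 0.625, 0.775 and 0.85, and the gains from 80% are 18.2, 14.3, 8.9 and 6.0 points. The three-visit gains need complete data at Cycles 4, 7 and 10.

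**4. Does GEE recover the loss by itself?** A simulation used 600 replicates, 30 per arm, three complete follow-up scores and a 0.5 SD effect. It compared a group-by-time GEE (baseline in the response, baseline means free to differ), a t-test on mean change, and baseline-adjusted regression.

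| ρ | GEE | change t-test | baseline-adjusted |
|---|---|---|---|
| 0.3 | 0.56 | 0.53 | 0.83 |
| 0.5 | 0.69 | 0.66 | 0.84 |
| 0.7 | 0.87 | 0.86 | 0.93 |

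The unconstrained GEE behaves much like the raw change score.

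**5. Attrition.** Patients leave the initial phase on progression (Section 7.1), and the follow-up schedule in Section 2.2 has no questionnaire. Assuming exponential PFS with the plan's medians, the numbers still progression-free (control, CC-486) are 30 × (0.727, 0.823) = 21.8 and 24.7 at Cycle 4, 15.8 and 20.3 at Cycle 7, and 11.5 and 16.7 at Cycle 10. At ρ = 0.5 the difference detectable with 80% power on change is 2.802 × √(1/n₁ + 1/n₂) SD; adjustment multiplies it by √0.75.

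| patients | change | adjusted |
|---|---|---|
| 30 and 30 | 0.72 SD | 0.63 SD |
| Cycle 4 | 0.82 SD | 0.71 SD |
| Cycle 10 | 1.07 SD | 0.93 SD |

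**6. N0/N1.** If the stratum explained 1%, 3%, 5% or 10% of residual variance (assumed), power would rise from 80% by 0.4, 1.2, 2.0 or 4.0 points. Nothing in the documents links nodal status to quality of life.

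**The case against.** The strongest reply is that 11.3.3 is silent on covariates and does not exclude them. A GEE with a common baseline mean, or one on change with baseline as a covariate, would fit its wording and recover most or all of the efficiency. This stands: a reader might infer that the plan has decided against adjustment, and the documents do not say so. But the only thing specified is a contrast in change, and the most direct model for it, an unconstrained group-by-time GEE, does not recover the gain (step 4).

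A reader might also infer that this trial loses 6 to 13 points of power. The documents do not support that. The range needs 80% reference power, ρ between 0.3 and 0.7, one visit and complete data, and none of these is stated for quality of life. Step 3 gives losses from about 3 to 18 points under other choices. None of the 6 to 13 points comes from N0/N1. Nor can the 0.72 and 0.63 SD for 30 per arm be taken as the trial's detectable differences, since step 5 shows larger ones once patients progress.

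Finally, the endpoint is secondary, unpowered and tied to no decision rule, and the unadjusted contrast is unbiased under randomisation with complete data. All of this is correct and limits the importance of the point.

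**Conclusion.** The point holds as an inexpensive gain in precision and a gap in specification; it is not an error that invalidates a result. The direction is firm: for any correlation below 1, apart from the negligible cost of one covariate, adjusting for the collected baseline is more precise than comparing change. The size is illustrative only: about 6 to 13 points at ρ 0.7 to 0.3 from an assumed 80% at one visit, and about 4 points at ρ = 0.8. The argument for N0/N1 is agreement with the stratified randomisation, with a gain that is unquantified and probably small. The primary PFS conclusion does not depend on any of this.

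**What to change.** State in Section 11.3.3:

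- **Outcome and terms.** A GEE for follow-up scores at Cycles 4, 7 and 10 with arm, cycle and arm-by-cycle terms, and with the pre-treatment baseline score and N0/N1 as covariates. Change from baseline may stay as the outcome, in line with the endpoint wording in Section 4.2: with baseline in the model, the treatment coefficient is identical.
- **Acceptable alternative.** Keep baseline in the response with one common baseline mean across arms, which retains patients who have only a baseline form. Name a working correlation other than independence: under independence the baseline scores would contribute nothing to the arm effect.
- **Baseline form.** Accept screening or Cycle 1 Day 1, as 11.3.3 already allows, with a rule for when both exist. Requiring the screening form would make some patients missing unnecessarily.
- **Missing baseline.** Say how it is handled in the main model, since multiple imputation is now planned only as a sensitivity analysis.
- **Reporting.** Give the adjusted between-arm difference with its confidence interval, and show raw change descriptively.

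The cost is a few sentences of SAP text. No new data, visits or patients are needed.

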11.3.4 Sample Size

The anecdotal time to progression without treatment is approximately 4 to 6 months. A feasible goal of 60 patients (30 in each arm) will provide 80% power to identify a 64% improvement in the median PFS from the null rate of 6 months assuming a one-sided type 1 error rate of 0.20, 24 months of accrual and a minimum of 12 months of follow-up while allowing for 10% loss to follow-up (protocol accruing for 6 months at the time of submission.

1-sided Type I error rate	Detectable HR (N = 60)
0.05	2.12
0.10	1.89
0.15	1.74
0.20	1.64

11.3.5 Safety Monitoring

Although the dose level is below the maximally tolerated dose, we will monitory the rates of grade 3/4 toxicity for individuals treated with CC-486. We would expect to observe grade 3/4 toxicities in 15% of patients. The goal is to ensure that the percentage of grade 3/4 toxicities remains below 30%. A Bayesian stopping guideline has been developed. The prior was chosen to be a Beta (1, 4), representing a 20% toxicity rate, which is at the high end of our expected value. The guidelines will recommend that the therapy be re-evaluated if the posterior probability of toxicity exceeding 30% is greater than 65%. Table 11.3.5.1 below summarizes the stopping guideline boundaries.

Table 11.3.5.1

Cohort size	Observed number of toxicities that trigger re-evaluation
6-9	4
10-12	5
13-15	6
16-18	7
19-21	8
22-24	9
25-27	10
28-31	11

The probability of triggering the stopping guidelines was assessed for a range of underlying toxicity rates based upon simulations with 5000 replicates (Table 11.3.5.2 below). In the expected range of toxicity, the probability of stopping early was less than 4.8%.

Table 11.3.5.2

True underlying toxicity rate	Probability of triggering stopping guideline boundaries
10%	1.2%
15%	4.8%
20%	14.1%
25%	32.2%
30%	54.1%
40%	89.6%
50%	99.1%

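### Section 11.3.5 does not say whether the toxicity guideline applies to the first five Arm A patients, and its claimed trigger probability below 4.8% contradicts its own table

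*Combined protocol and SAP*

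**What the plan says.** Section 11.3.5 (Safety Monitoring) sets the expectation, "We would expect to observe grade 3/4 toxicities in 15% of patients", and the aim, "The goal is to ensure that the percentage of grade 3/4 toxicities remains below 30"%. On the prior it says: "The prior was chosen to be a Beta (1, 4), representing a 20% toxicity rate, which is at the high end of our expected value". Its trigger is: "The guidelines will recommend that the therapy be re-evaluated if the posterior probability of toxicity exceeding 30% is greater than 65"%. No minimum cohort is attached to that sentence.

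Table 11.3.5.1 lists cohort sizes against the "Observed number of toxicities that trigger re-evaluation". Its rows are 6-9: 4; 10-12: 5; 13-15: 6; 16-18: 7; 19-21: 8; 22-24: 9; 25-27: 10; 28-31: 11. There is no row below six.

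Table 11.3.5.2 gives the probability of a trigger, "based upon simulations with 5000 replicates": 1.2%, 4.8%, 14.1%, 32.2%, 54.1%, 89.6% and 99.1% at true rates of 10%, 15%, 20%, 25%, 30%, 40% and 50%. The text sums this up as: "In the expected range of toxicity, the probability of stopping early was less than 4.8"%. The synopsis plans 30 patients per arm.

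**The concern.** There are two inconsistencies within one section.

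First, the rule is written for any number of patients, while the table that is meant to summarise it is silent on the first five. If the rule can trigger below six, someone working from the sentence and someone working from the table would act differently on the same data, at the point where least is known about the drug in this population.

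Second, the summary sentence claims a trigger probability below 4.8% across the expected range, yet the section places 20% at the high end of that range and its table prints 14.1% there. A monitoring body that relied on the sentence would underrate how often the guideline fires when toxicity is still well under the 30% limit.

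**Working it through.** **Inputs** (Section 11.3.5 and synopsis): prior Beta(1,4); trigger when P(rate > 0.30 | data) > 0.65; 30 Arm A patients. I assume one yes/no toxicity outcome per patient and a look after every patient.

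**1. Reproduce the printed boundaries.** With x toxicities in n patients the posterior is Beta(1+x, 4+n−x). The boundary is the smallest x whose upper tail at 0.30 exceeds 0.65. Every printed row from n = 6 to 31 reproduces. The close cases pin the threshold down: 3/6 gives 0.6496 (no trigger), 4/9 gives 0.654 and 11/31 gives 0.652 (both trigger).

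**2. Apply the same rule below six.** For 2/2 the posterior is Beta(3,4), so P(rate > 0.30) = 0.7⁶ + 6(0.3)(0.7⁵) + 15(0.3²)(0.7⁴) = 0.1176 + 0.3025 + 0.3241 = 0.744. In the same way:

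| Data | Posterior P(rate > 30%) | Trigger? |
|---|---|---|
| 1/1 | 0.528 | no |
| 2/2 | 0.744 | yes |
| 2/3 | 0.647 | no |
| 3/3 | 0.874 | yes |
| 3/4 | 0.806 | yes |
| 3/5 | 0.730 | yes |

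The implied rows are cohort 2: 2 and cohorts 3-5: 3.

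**3. How often this matters within five patients.** The stated rule fires with probability p² + 2p(1−p)[3p²(1−p) + p³] + (1−p)²p³. At p = 0.30 this is 0.0900 + 0.42 × 0.216 + 0.49 × 0.027 = 0.194. At 15%, 20%, 40% and 50% it is 4.0%, 7.8%, 35.2% and 53.1%. The table has no boundary there.

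**4. Trigger probability over the whole arm.** This is an exact binomial recursion that removes paths once they cross the boundary, with N = 30. The margin is the 95% half-width for 5000 replicates, 1.96√(q(1−q)/5000), with q the printed value.

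| True rate | Printed | Margin (points) | First look at 6 | Looks from the start |
|---|---|---|---|---|
| 10% | 1.2% | 0.3 | 1.1% | 2.3% |
| 15% | 4.8% | 0.6 | 5.0% | 7.3% |
| 20% | 14.1% | 1.0 | 14.1% | 17.2% |
| 25% | 32.2% | 1.3 | 29.4% | 32.6% |
| 30% | 54.1% | 1.4 | 49.0% | 51.7% |
| 40% | 89.6% | 0.9 | 83.7% | 84.7% |
| 50% | 99.1% | 0.3 | 97.7% | 97.8% |

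The printed values at 10%, 15% and 20% match a first look at six, not looks from the start. At 25%, 30% and 40% the printed values exceed the first-look-at-six values by 2.8, 5.1 and 5.9 points, well beyond simulation error. Running to N = 31 does not close the gap (30.1%, 50.4%, 85.2%). A first look at six with about 40 patients fits the whole column: 1.1%, 5.0%, 14.8%, 32.0%, 54.3%, 89.5%, 99.2%. That the simulation used a larger cohort is an inference; the section does not state its cohort size.

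**5. The summary sentence.** At 15% the table prints 4.8%, which is not below 4.8%. At 20% it prints 14.1%, and 14.1/4.8 is about 2.9 times the claimed ceiling.

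**The case against.** The best defence is that six is a deliberate minimum cohort. Prior, threshold and all eight rows agree exactly from six onward, and the printed figures at 10%, 15% and 20% fit a first look there. This is plausible, and it would make the first defect a missing clause rather than an arithmetic error. But the section does not say so, and the rule as worded has no lower limit.

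A reader might infer that three toxicities in the first three patients would go unreviewed. The documents do not support that. Section 6.2 requires fatal and serious unanticipated events to be reported within 24 hours, Section 6.3.1 sends every serious event to the drug supplier within 24 hours, Section 10.3 provides Safety Monitoring Committee oversight, and Section 10.5 sets monthly safety teleconferences. The guideline itself only recommends re-evaluation. What stands is that none of these supplies a numerical boundary or settles when the guideline starts.

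The effect on overall detection is also small. Over 30 patients the early rows move the trigger probability from 49.0% to 51.7% at a true 30% rate and from 83.7% to 84.7% at 40%. The difference is mainly one of timing. If more than five Arm A patients have already been evaluated (Section 11.3.4 mentions six months of accrual at submission), the early rows matter for the record more than for conduct.

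On the summary sentence, the expected range could be read as up to 15%, with the 20% remark only explaining the prior. Then the slip is strictly below instead of at most. But describing 20% as "representing a 20% toxicity rate, which is at the high end of our expected value" makes the wider reading fair, and the sentence is inaccurate on either one.

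**Conclusion.** Both inconsistencies hold. Text and table disagree on whether the guideline applies to the first five Arm A patients, and the stated rule triggers there at 2/2, 3/3, 3/4 and 3/5. The summary sentence is wrong against its own table: 4.8% at 15% and 14.1% at 20%. In addition, the printed trigger probabilities at 25%, 30% and 40% do not reproduce for the planned 30 patients, so correcting only the lower entries would leave a column computed on two bases.

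The printed boundaries from six upward are correct. A reader might also take 14.1% as the chance that a given trigger is a false alarm. It is not: it is the chance of a trigger when the true rate is 20%.

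The posterior values depend only on the stated prior and threshold. The trigger probabilities also assume a look after each patient and 30 evaluable Arm A patients.

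**What to change.** 1. Reconcile rule and table. Either state that the guideline is first evaluated at six patients, or add the rows the stated rule implies (cohort 2: 2; cohorts 3-5: 3). Which applies is for the sponsor to decide.
2. Recompute all of Table 11.3.5.2 for that first look and 30 Arm A patients, and state both beside the table. The last two columns of the table in step 4 of the working give the exact values for each option.
3. Replace the claim of a probability below 4.8% with the figures at both 15% and 20%: 5.0% and 14.1% with a first look at six, or 7.3% and 17.2% with looks from the start.

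The cost is one clause or two table rows, a rerun of one table, and one sentence. The stated chances of detecting true rates of 25% to 40% become less favourable, except that with looks from the start the 25% figure is essentially unchanged (32.6% against the printed 32.2%). Adding the early rows also raises the trigger probability at a true 15% rate from 5.0% to 7.3%.

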This trial is for patients with resected pancreatic adenocarcinoma who have concluded adjuvant therapy or were deemed unable to receive adjuvant therapy with an elevated CA 19-9 or node positive or margin positive disease. CA 19-9 elevation is defined as two levels > the institutional upper limit of normal (ULN) taken at least 2 weeks apart. These levels should be measured after adjuvant therapy has concluded or upon the decision that adjuvant therapy will not be offered. Patients will be randomized to one of two arms. Subjects enrolled due to node + disease or R1 resection must be able to undergo randomization within 3 months of finishing adjuvant therapy or the decision that they are unable to take adjuvant therapy has completed. Group A, the treatment arm, will be started on CC-486. Group B, the control arm, will receive no additional therapy. In both arms, CA 19-9 will be followed and CT scans (or MRI, if clinically indicated) will be done every three months. When patients have visible disease recurrence on imaging, CC-486 will be stopped and both groups will start first-line chemotherapy.

Assuming the maximum accrual with a goal of 2-3 subjects accrued per month, we estimate enrollment duration of 24 months with an additional 12 months for follow-up with concurrent data analysis and manuscript preparation.

TOTAL SAMPLE SIZE:

Maximum 60 patients, with 30 patients in each of the two arms.

[figure not shown]
DRUG SUPPLIES:

For study participants, Celgene Corporation will provide CC-486

DOSING REGIMEN:

Treatment Arm	DRUG	DOSE	FREQUENCY	# of CYCLES	Route
Α	CC-486	300 mg total, three 100 mg tablets	Daily, Days 1- 21, Q28 Day cycles	12 cycles and then follow-up	Oral
В	Observation	N/A	N/A	12 cycles. Follow-up 1 will be collected 3 months after Cycle 10.	N/A

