5.3.2.2 Arm A for first 12 cycles

Arm A patients will be evaluated on Day 1 of every cycle with a physical examination, ECOG performance status, vital signs, weight, CBC with differential, research blood and serum chemistry and hepatic panel. Arm A patients will also complete an assessment of adverse events and reporting of current medications/procedures on Day 1 of every cycle.

Arm A patients will complete a CA 19-9, quality of life assessment and CT scan on Day 1 of every third cycle beginning at Cycle 4.

Arm A subjects will be evaluated for adverse events on Day 1 of each cycle with the NCI CTCAE v4.0 (http://ctep.info.nih.gov) used as a guide for the grading of severity. For Arm A patients, doses will be reduced for hematologic and other non-hematologic toxicities that can be attributed to the study drug. Dose adjustments are to be made according to the system showing the greatest degree of toxicity. When a dose reduction is required for Day 1 of any cycle, no dose re-escalation will be permitted for the duration of study treatment.

NOTE: Arm B patients will not be evaluated for adverse events as they do not receive the study agent.

Criteria to Initiate Treatment

In Arm A, a new course of treatment may begin on the scheduled Day 1 of a new cycle if:

- Absolute neutrophil count $\geq 1500/\text{mm}^3$
- Platelet count $\geq 100,000/\text{mm}^3$
- Serum creatinine levels < 2 mg/dL
- Serum bilirubin levels $\leq 1.5 \text{ mg/dL}$.
- AST (SGOT) and ALT (SGPT) \leq 2.5 x the institutional upper limit (ULN) of the normal range
- Any other drug-related adverse events that may have occurred must have resolved to < Grade 2 severity except grade 2 anorexia and any correctable metabolic abnormality.
- No evidence of visible disease recurrence on imaging (if indicated per Study Schedule, Section 2, to be done prior to cycles 4, 7, and 10)

If these conditions are not met on Day 1 of a new cycle, the subject will be evaluated weekly and a new cycle of treatment will not be initiated until the toxicity has resolved as described above utilizing the dose modifications as depicted below. If the study drug has to be held for > 28 days, study treatment will be discontinued.

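### The toxicity guideline sets no minimum observation time for a patient to count, so read literally it triggers later and less often than with complete outcomes, and Table 11.3.5.2 should be redone

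*Combined protocol and SAP*

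**What the plan says.** Section 11.3.5 describes the population monitored: "we will monitory the rates of grade 3/4 toxicity for individuals treated with CC-486". It gives the expected rate, "We would expect to observe grade 3/4 toxicities in 15% of patients", sets 30% as the level to stay below, and specifies the prior: "The prior was chosen to be a Beta (1, 4), representing a 20% toxicity rate". The trigger is stated as: "The guidelines will recommend that the therapy be re-evaluated if the posterior probability of toxicity exceeding 30% is greater than 65" percent. Table 11.3.5.1 has two columns, cohort size (rows from 6-9 to 28-31) and "Observed number of toxicities that trigger re-evaluation". Table 11.3.5.2 gives the chance of triggering by true rate, from 5,000 simulated replicates, without describing accrual or toxicity timing.

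The section does not say who belongs to the cohort at a given look, how long a patient must have been observed, over what period a toxicity counts, or when the looks occur. No other section supplies these.

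Elsewhere, the synopsis (1.1) plans 30 patients in Arm A, up to 12 cycles, and accrual as follows: "Assuming the maximum accrual with a goal of 2-3 subjects accrued per month". Section 5.2.9.1 sets 28-day cycles. Section 5.3.2.2 says: "Arm A subjects will be evaluated for adverse events on Day 1 of each cycle". Toxicity is therefore sought through a course of about 11 months.

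**The concern.** A Beta-binomial rule treats each patient in the denominator as having a known outcome. When toxicity can appear at any time over many months, a patient dosed last week has no known outcome. Counting that patient as toxicity-free pulls the posterior towards safety, and it does so most at small cohorts, where newly started patients are the largest share.

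The boundaries show the effect. Four toxicities in 9 patients give Beta(5, 9) and P(rate > 30%) = 0.654, which triggers. If a tenth patient starts before the fourth toxicity appears, the posterior is Beta(5, 10) and the probability is 0.584, which does not. The tenth patient has supplied no safety information, yet the signal is gone.

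At stake are the number of patients started on CC-486 before a too-toxic regimen is flagged, and whether the protection stated in Table 11.3.5.2 is delivered.

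**Working it through.** **1. The plan's own figures**

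Taking the smallest k with P(Beta(1+k, 4+n−k) > 0.30) > 0.65 for n = 6 to 31 gives 4, 5, 6, 7, 8, 9, 10, 11 for the eight rows. Table 11.3.5.1 reproduces exactly.

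Table 11.3.5.2 was checked by exact binomial recursion, with outcomes known at once, a look after each patient from the 6th, and a cap of 30:

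| True rate | Stated | Exact, 30 patients |
|---|---|---|
| 10% | 1.2% | 1.1% |
| 15% | 4.8% | 5.0% |
| 20% | 14.1% | 14.1% |
| 25% | 32.2% | 29.4% |
| 30% | 54.1% | 49.0% |
| 40% | 89.6% | 83.7% |
| 50% | 99.1% | 97.7% |

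So 54.1 − 49.0 = 5.1 points at 30%, and 89.6 − 83.7 = 5.9 points at 40%, are missing before any delay is considered. A cap of 31 does not close the gap. The stated figures match within 0.7 points if the rule runs on to about 40-42 patients, more than Arm A will have.

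**2. Size of the early shortfall**

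Inputs: 30 Arm A patients over 24 months is 1.25 per month (1 to 1.5 per month from the stated 2-3 overall). When the 10th patient starts, the first has been observed for 9 / 1.25 = 7.2 months and the tenth for none.

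With onset distribution F and regular entry, the expected observed/true ratio when patient n starts is (1/n) × Σ F(i/1.25), for i = 0 to n−1. As a hand check, assume onset uniform over 3 months:
- At n = 6, observation times are 0, 0.8, 1.6, 2.4, 3.2 and 4.0 months, so F is 0, 0.267, 0.533, 0.8, 1 and 1. The sum is 3.6, the ratio is 0.60, and the shortfall is 40%.
- At n = 12 the sum is 9.6, the ratio is 0.80, and the shortfall is 20%.

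Onset timing is an assumption throughout. Across 1 to 1.5 patients per month, the shortfall if all toxicity falls in cycle 1 is 17-21% at n = 6 and 8-11% at n = 12. If toxicity is uniform over 12 cycles, it is 77-85% and 50-67%.

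**3. Effect on triggering**

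Simulation (2,500-4,000 replicates per scenario): 30 patients at 1.25 per month; treatment to 12 cycles or progression (exponential, median 9.84 months, the alternative in section 11.3.6); each patient has a toxicity with probability p, uniform over the stated window or the treatment time if shorter; boundaries checked at every entry and every toxicity from n = 6; all treated patients counted.

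| | Outcomes at once | First 2 cycles | Over 6 cycles | Whole course |
|---|---|---|---|---|
| Observed/true at 10th patient | 1 | 0.85 | 0.66 | 0.50 |
| Observed/true at 20th patient | 1 | 0.93 | 0.83 | 0.74 |
| Trigger chance, true 30% | 49% | 46% | 39% | 33% |
| Median treated at trigger, true 30% | 9 | 10 | 14 | 21 |
| Trigger chance, true 40% | 84% | 82% | 78% | 74% |
| Median treated at trigger, true 40% | 9 | 9 | 13 | 18 |

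Medians are among trials that trigger.

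**4. Sensitivity**

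A separate set of onset assumptions (from exponential with mean 1 month to uniform over 11 months, no early end of treatment) gives:

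| True rate | Trigger chance, at once | Trigger chance, delayed | Mean treated, at once | Mean treated, delayed |
|---|---|---|---|---|
| 30% | 49.0% | 28-45% | 21.2 | 22.6-28.8 |
| 40% | 83.7% | 73-82% | 14.2 | 15.6-25.6 |
| 50% | 97.7% | 95-97% | 9.6 | 10.6-21.5 |

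**The case against.** The strongest objection is that the plan never says that every treated patient is in the denominator. The phrase about individuals treated with CC-486 names a population, and a sensible team might count only patients with adequate follow-up. That is correct: the documents leave the cohort undefined, and a reader should not infer a stated rule. But nothing in them excludes a just-started patient, and the missing definition is what needs repair.

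Three stronger readings are tempting and not supported.
- One might quote a single percentage for the shortfall. No section gives toxicity timing, so any such figure is an assumption; the cases above run from about 8% to 85% for cohorts of 6 to 12.
- One might conclude that a toxic regimen would escape the guideline. Later events from earlier patients still count, and at a true 50% the trigger chance stays at 95-97%. If toxicity is early, the median number treated at the trigger barely moves.
- One might blame the whole gap to Table 11.3.5.2 on staggered entry. At a true 30%, 5.1 points of it exist with no delay; staggered entry adds about 3, 10 or 16 points (49 minus 46, 39 or 33).

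The guideline is also not the only safeguard. It only recommends re-evaluation, and the protocol has per-patient toxicity rules (Table 5.3.1, section 5.4), 24-hour reporting of serious events to the drug supplier (6.3.1), Safety Monitoring Committee oversight (10.3) and monthly safety calls (10.5). These limit the harm. They do not make the quantitative rule perform as stated.

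**Conclusion.** The concern holds as a conditional one. The plan sets no observation requirement for a course of up to 12 cycles. If it is followed on its natural literal reading, the observed toxicity rate is biased low at early looks and the trigger comes later and less often. Near the 30% limit the loss is small if toxicity is confined to the first 2 cycles (46% against 49%) and material if it is spread out (39% or 33%, with a median of 14 or 21 already treated instead of 9). At 40% it is about 2 to 10 points. At 50% the chance of triggering is nearly unchanged, although with late onset more patients are treated first.

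Separately, the 54.1% and 89.6% stated at 30% and 40% are not attained with 30 Arm A patients even under instant outcomes.

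The direction follows from the literal reading alone. The sizes rest on assumed onset times, regular entry at 1.25 per month, and checks at every entry and every toxicity. The change should be made; it is inexpensive and bears on safety monitoring.

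**What to change.** In section 11.3.5:
- Define the cohort as Arm A patients who have had a grade 3/4 toxicity, or have completed a stated minimum observation period, or have ended CC-486. The study team should choose and justify the period; 3 cycles is used here only as an example.
- State that the boundaries are checked at each toxicity and each time a patient joins the cohort. The boundaries themselves can stay.
- Re-run Table 11.3.5.2 for 30 patients with staggered entry over a stated range of onset times, and replace the current figures.

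With the 3-cycle example, the simulated trigger chance is about 54%, 49% and 43% at a true 30% for the three onset patterns, and about 88%, 83% and 79% at 40%.

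The costs should be stated in the plan. Toxicities enter at once and non-toxicities only after the waiting period, so early rates are biased somewhat upward. The false-trigger chance at a true 15% is about 7%, 5% and 3%, against about 5% with instant outcomes. In the wider set of onset assumptions it is 1.3-7.5%, against 0.4-4.3% when all treated patients count. A patient who leaves treatment early without toxicity still counts in full, and late-onset toxicity is only partly recovered. No new visits or data are needed, and a false trigger leads to a re-evaluation, not automatic closure.
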